Prior/Concomitant Medications	X	X	X	X	X	X	X	X	X	X	X	X	X	X	X	X
MINI International Neuropsychiatric Interview	X															
Columbia Suicide Severity Rating Scale (C-SSRS) – Clinician Administered	X ^a															
Hospital Anxiety and Depression Scale (HADS)	X	X	X	X	X	X	X	X	X	X	X	X	X	X	X	X
Urine Pregnancy Test (females only) ^a	X		X			X			X			X			X	
Biochemical Measures of Substance Use																
Carbon Monoxide	X	X	X	X	X	X	X	X	X	X	X	X	X	X	X	X
Urine Drug Screen (instant-read) ^g	X	X	X	X	X	X	X	X	X	X	X	X	X	X	X	X
Urine Cotinine (lab assay and instant-read) ^g	X	X	X	X	X	X	X	X	X	X	X	X	X	X	X	X
Urine Cannabinoids (lab assay)* ^g	X	X	X	X	X	X	X	X	X	X	X	X	X	X	X	X
Substance Use Assessments																
Substance Use History	X															
Timeline Follow-Back	X	X	X ^b	X ^b	X ^b	X ^b	X ^b	X ^b	X ^b	X ^b	X ^b	X ^b	X ^b	X ^b	X ^b	X
Tobacco																
Fagerström Test for Nicotine Dependence (FTND)	X						X ^f			X ^f					X	X
Stages of Change - Short Form (Tobacco)	X															
Readiness/Confidence/Interest to Quit Smoking	X	X	X													
Minnesota Nicotine Withdrawal Scale	X		X	X	X	X	X	X	X	X	X	X	X	X	X	X
Modified Cigarette Evaluation Questionnaire	X		X	X	X	X	X	X	X	X	X	X	X	X	X	X
Questionnaire on Smoking Urges – Brief	X		X	X	X	X	X	X	X	X	X	X	X	X	X	X
Smoking Abstinence Self-Efficacy	X						X ^f			X ^f					X	X
Wisconsin Predicting Patient's Relapse	X															
Quit Smoking Methods															X	X
Cannabis																
Cannabis Quantification	X ^c															
Cannabis Use Disorder Identification Test-Revised	X															X
Cannabis Quit Interest	X ^d		X				X ^f			X ^f					X	X
Marijuana Craving Questionnaire	X		X	X	X	X	X	X	X	X	X	X	X	X	X	X
Modified Lyons Battery for Subjective Effects	X		X				X ^f			X ^f					X	X
Marijuana Problems Scale	X		X				X ^f			X ^f					X	X
Cannabis Withdrawal Scale	X		X				X ^f			X ^f					X	X
Marijuana Motives Measure	X															
Patterns of Co-Use Assessment	X		X				X ^f			X ^f					X	X
Acceptability Surveys																
Medication Acceptability Survey															X	
Participant Satisfaction Survey																X
Co-Use Treatment Preferences Survey																X
Medication Safety/Adherence																
Vital Signs ^a																
Blood Pressure, Pulse	X			X												
Height [screening]																
Weight [screening, Weeks 12 and 26]																
Adverse Events	X	X	X	X	X	X	X	X	X	X	X	X	X	X	X	X
Medication Adherence																
Pill counts				X	X	X	X	X	X	X	X	X	X	X	X	X
Pillsy cap				X	X	X	X	X	X	X	X	X	X	X	X	X
REDCap videos				X	X	X	X	X	X	X	X	X	X	X	X	X
Mobile Surveys																
Daily Diaries	X ^e	X ^e	X ^e	X ^e	X ^e	X ^e	X ^e	X ^e	X ^e	X ^e	X ^e	X ^e	X ^e	X ^e	X ^e	
REDCap Medication Videos	X	X ^e	X ^e	X ^e	X ^e	X ^e	X ^e	X ^e	X ^e	X ^e	X ^e	X ^e	X ^e	X ^e	X ^e	
EMA Mobile Sessions (ilumivu)	X		X												X	

SC=Screening/Assessment; T=Training Visit; M=Medication Dispensation (Day 0); F/U=Post-Medication Follow-Up

^a=can be completed as needed throughout the study (at any study visit)^b=completed at weekly visits when daily dairies are missed^c=conducted at screening and then throughout the study when new methods of cannabis use are endorsed; should be completed for any ppt who endorses cannabis use (even if NOT categorized as a co-user)^d=administered at screening as part of a cannabis history questionnaire, and then administered alone at subsequent visits

administered daily (dairies) or twice daily (med videos)

^e=administered daily (dairies) or twice daily (med videos)^f=Study assessments completed at Weeks 4 or 8 may be completed at Weeks 5 and 9^g=Saliva sample may be collected in addition to other biochemical measures for quality improvement purposes, will not be used for research purposes

*=Saliva sample will also be collected for 10 study participants to assess for cannabinoids

Participant Compensation: Participants will be compensated \$40 for the Screening visit and \$30 per visit for Training, Day 0, other weekly visits (13 visits) and/or early termination (ET) that occurs at any point other than during the Week 12 window (\$50 for Week 12 window visits). They will be compensated \$50 for the end-of-treatment visit (Week 12), and \$50 for the 6-month follow-up visit (Week 26). Compensation is based on completion of all study procedures. Partial compensation may be given for partially completed study visits. For example, payment amounts for remote visits will be contingent on return of the urine sample to study staff at the next in-person study visit. Compensation will be delivered contingent on tobacco abstinence at weekly visits starting at Week 2 (\$20 per visit; \$220 possible). Participants will be compensated for completing daily dairies and medication videos during the 12-week treatment phase. Compensation amount for remote surveys and videos will be based on the percentage of videos and morning reports completed over the past week and will be paid at weekly visits. The compensation scheduled based on the percentage of completed sessions is shown to the right (\$300 maximum for $\geq 90\%$ compliance over 12 weeks). Participants may earn a total of \$1,050 for study participation and completion of all study procedures.

Medication Videos and Logs (% completed each week)	Payment
90-100% compliance	\$25
80-89.9% compliance	\$20
70-79.9% compliance	\$15
50-69.9% compliance	\$10
30-49.9% compliance	\$5
<30% compliance	\$0

Payment for study visits will be made using a pre-paid debit card, called a ClinCard. It works like a bank debit card and participants may use the card to purchase goods or services everywhere Debit MasterCard is accepted. Participants will be given or mailed a ClinCard at the beginning of the study. Each time they receive payment for participation in this study, the money will be added to the card, as outlined in the payment schedule above. Details of the debit card system are explained on an additional sheet.

If an Unscheduled Visit is required during study participation, the participant will be compensated \$10/visit in return for the time and travel demands asked of them.

Additionally, Respondent-Driven Sampling (RDS) will be used to enhance recruitment. The RDS sampling methodology is based on recruiting the eligible friends and acquaintances of each participant so that the sample “snowballs.” Each eligible participant who is enrolled into the study, and agrees to take part in this recruitment assistance, is eligible to receive compensation for successful referrals. A referral will be instructed to call the study team to be screened for eligibility. If that person successfully enrolls into the study (i.e., completes the Day 0 visit and begins taking study medication), the participant who referred them can receive \$30 in compensation for each eligible participant that is referred and enrolled in the study. The research team has used these methods successfully in the past.

In addition to compensation described above, participants enrolled in the EMA supplement portion of the study will be compensated contingent on completion of EMA surveys. For each 1-week burst of EMA data collection, participants may earn a maximum of \$70 for completion of sessions on a sliding scale. A maximum of \$280 can be earned over the four, 1-week bursts of EMA data collection.

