B1. Study Overview. This proposed prospective tobacco cessation study will evaluate the impact of concurrent cannabis use and severity on tobacco abstinence among co-users and assess changes in cannabis use during treatment. Adult tobacco users (ages 18-40) who are motivated to quit smoking will be recruited. Cannabis co-users will be oversampled (2:1) and will be compared to tobacco only participants (using appropriate propensity score models). All participants will receive first-line tobacco cessation pharmacotherapy (varenicline) paired with a behavioral intervention to bolster abstinence rates (contingency management and psychosocial counseling) for a standard 12-week treatment period. Cannabis use will not be targeted with treatment. This is not a treatment outcome study per se and thus we are not evaluating (with a control group) an intervention. Rather, cannabis use status (co-use vs. not) is our independent variable. Biochemical verification of tobacco and cannabis use will be collected at screening and throughout the 12-week treatment period in addition to daily self-reports of use. Specifically, this study will: 1) examine the impact of cannabis co-use on tobacco cessation among co-users compared to tobacco only users (Aim #1); 2) with the use of frequent measurement, assess changes in cannabis use (among co-users) during tobacco treatment and determine if profiles of changes in cannabis use emerge (i.e., compensatory use, reduction, no change) (Aim #2); and 3) assess for a dose-dependent impact of cannabis use severity on tobacco cessation outcomes among co-users (Exploratory Aim).

It should be noted that while this is not a randomized and blinded study (cannabis co-use status will be known to research staff), it is important to not bias the results of the study. The hypothesis is that cannabis co-use will adversely impact tobacco cessation, but it's important to the scientific integrity of this study to obscure that hypothesis from study participants and manage biases with research staff. Staff will be educated about introducing bias into the study and methods to manage bias in non-randomized and non-blinded trials. For research participants, the aim of the study will intentionally broad and ambiguous to not

overtly influence their behavior and tobacco quit attempt. The title of the study and consent document, therefore, are not as specific as they would normally be to maintain the integrity of this research.

B2. Preliminary Studies.

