Quit interest in co-users. Cross-sectional survey data collected from our group assessed quit interest and compensatory drug use in co-users (81). Among an online sample ($N=182$), interest in quitting tobacco was high (7.1 ± 2.9 ; 10-point scale), while interest in quitting cannabis was low (2.4 ± 2.3 ; 10-point scale). This study also found that among participants who had ever tried to quit tobacco (80%), half self-reported increases in their cannabis use during the quit attempt. While these data were retrospective, this result further emphasizes the importance of measuring cannabis use changes during tobacco treatment. These data also suggest that the proposed design will be acceptable to co-users given that tobacco treatment will be provided while not addressing cannabis use, as co-users show low interest in cannabis cessation.

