Behavioral strategies will also be used to promote tobacco abstinence. First, psychosocial counseling will be administered at the training visit and Day 0 in preparation for the target quit date (Day 8). During the treatment phase, brief counseling (<5-10 minute) will be provided at all weekly visits by trained research staff and will include motivational enhancement for medication adherence and tobacco cessation. The content of counseling will be skills-based and focused on enlisting social support, recognizing smoking triggers, managing craving/withdrawal/stress, etc. Cannabis use will not be addressed as part of counseling. If the participant expresses a desire to reduce/quit using cannabis, standard information and resources will be provided, but this will be kept minimal to avoid researcher-imposed impact on cannabis use. Participants will be encouraged to pursue desired cessation, but will be reminded that the current study is focused on tobacco cessation.

Mobile sessions: Each morning during the 12-week study (and one week leading up to Day 0), participants will receive a text message and email link to complete their daily diary. Daily diaries will be administered and data will be managed through the Research Electronic Data Capture system (REDCap) (82). Our research team has previously used daily diaries through REDCap (77). Standard questions will be administered regarding substance use that occurred during the prior day (midnight to midnight of the past calendar day).

Weekly Visits (Weeks 1 - 12): Participants will be asked to complete weekly visits for the next 11 weeks. During visits, research staff will review compliance with daily diaries and discuss medication adherence over the past week (assessed through REDCap medication videos, smart bottle caps, daily diaries, and pill counts). Medication tolerability will be systematically assessed, and medical clinicians will be contacted if any potentially related adverse events are reported. Self-report assessments will be administered (e.g., craving, withdrawal, etc.). Brief cessation counseling will be conducted and bonus compensation (i.e.,

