10.0 Statistical Analysis and Data Management

Analytic Strategy.

Power and sample size. The proposed study is powered to detect a meaningful difference in end of treatment tobacco abstinence between cannabis co-users and tobacco only users. Secondarily, the study will assess the relationship between cannabis use patterns during treatment and nicotine dependence severity in co-users. Specific Aim #1: Examine the impact of cannabis co-use on tobacco cessation outcomes among co-users compared to tobacco only users. Hypothesis 1: Co-users will have lower rates of 7-day point prevalence abstinence from tobacco at the end of treatment (Week 12) compared to tobacco only users. In a cross-sectional survey of national household data (51), tobacco cessation was reported among 65.5% of respondents who endorsed no cannabis use as compared to 21.8% of tobacco cessation in those reporting current cannabis use ($\Delta=43\%$). Studies examining the efficacy of varenicline for tobacco cessation (108, 109) noted near 50%-point prevalence abstinence at treatment conclusion (Week 12) in the varenicline-treated group. Finally, in our recently completed adolescent varenicline trial (U01 DA0317779), youth cannabis co-users reported point prevalence tobacco abstinence in 20% of participants at Week 12 and 43% in those who use tobacco only (analysis with all available data). The proposed R01 study intends to apply a successful tobacco treatment (varenicline) paired with contingency management in treatment-seeking smokers. Assuming a similar abstinence rate in tobacco only users (45%) and a successful abstinence rate in participants who are cannabis co-users as compared to the adolescent study (20%; $\Delta=25\%$), to achieve 80% power with a 5% type 1 error rate, a sample of 82 participants in the cannabis co-using cohort and 41 in the tobacco only cohort. However, to account for the inclusion of 2 study sites in the design, an additional fixed factor of site will be included in the analytic models. Although we hope that equal proportions of co-users and non co-users present at each site, we understand that the fundamental differences between the Charleston metro area, Pickens County SC, and Florence exist and may cause some correlation between co-use group and study site. Assuming that the proportion of variance in co-use groups due to study site and other covariates may be moderate ($R^2=0.25$) and that attrition will not exceed 25%, we have adjusted our study sample size to account for this scenario. This increases our randomized sample to a total of 208 (139 cannabis co-users and 69 tobacco only users) accounting for both site correlations with co-use group and anticipated attrition. If site correlations with study outcomes or attrition are lower than pre-specified, our statistical power will exceed 80%. Specific Aim #2: Among co-users, assess changes in cannabis use during tobacco cessation treatment. Hypothesis 2: Co-users with moderate to high severity of nicotine dependence will demonstrate increases in concurrent cannabis use, while lower severity of nicotine dependence will yield no changes in cannabis use. To attain adequate power to assess Aim #2, a within co-use cohort comparison, the study will oversample the cannabis co-use cohort as compared to the tobacco only cohort (2:1). At screening, nicotine dependence will be assessed via the Fagerström Test for Nicotine Dependence (FTND) (92) and categorized accordingly: low nicotine dependence (0-4), medium or high nicotine dependence (5-6; 7-10). Cannabis use during the final 4 weeks of study treatment as compared to baseline use will be assessed among co-users. Based on our preliminary data from an ongoing adult tobacco cessation trial (R34 DA042228), we have nearly equivalent numbers of participants falling into low and moderate/high nicotine dependence categorizations (Mean=4.5; Median=5). Therefore, we anticipate ~40% will have medium/high nicotine dependence. With 208 participants, 139 in the cannabis co-use cohort (104 completers), we will achieve 80% power with a type 1 error rate of 5% to detect a between group cannabis use difference of Cohen's $d\approx0.6$ (Med/High nicotine dependence vs. low nicotine dependence).

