Primary Study Aims: Aim 1: To assess the difference in the log-odds of abstinence from tobacco at the end of treatment (Week 12) between baseline cannabis co-users compared to tobacco only participants, augmented inverse probability weighted logistic regression models will be developed. The inverse of the conditional probability of being in the cannabis co-use cohort will be included in the model to account for inherent imbalances between study groups and to reduce bias by resembling a randomized controlled trial. In addition to the inverse propensity weights, AIPW methods incorporate a covariate and study site adjusted model for the study group outcome (114). Aim 2: To assess the association of baseline nicotine dependence severity (Med/High nicotine dependence vs. low nicotine dependence) with cannabis use rates during study treatment, generalized linear mixed effects models will be assessed with cannabis use rates and amounts during the final 4 weeks of treatment as the primary indicator of cannabis use severity and nicotine dependence group as the primary model predictor. In addition to grouping by nicotine dependence severity, continuous levels of dependence severity (FTND score) will be modeled to assess possible linear and quadratic relationships between dependence severity and cannabis use. Following examination of the differences in end of treatment cannabis use rates based on baseline nicotine dependence, rates of cannabis use will be assessed by group (nicotine dependence severity) over all weekly study visits to determine if those with increased dependence severity exhibit a different trajectory (slope and pattern) of cannabis use during the entire study treatment. Model-based means and associated standard errors will be used to test group level differences. Exploratory Aim: To assess the relationship between baseline cannabis use severity and tobacco outcomes, generalized linear mixed effects models will be developed with weekly 7-day point prevalence abstinence from tobacco as the primary model outcome. In addition to tobacco abstinence, weekly average cigarettes per day will be examined as an indicator of use reduction differences over time. Longitudinal patterns in tobacco abstinence and use amounts will be modeled through the inclusion of baseline cannabis use severity indicators, study visit, and baseline tobacco use rates as model covariates. Additionally, differential effects over time will be examined with the inclusion of the interaction of cannabis use severity and study visit. Model-based means and associated standard errors will be used to test group level differences across the study treatment.

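### The Aim 2 cannabis models do not pre-specify the screening cannabis quit interest score, so self-chosen cannabis reduction can add variance to the nicotine-dependence contrast and bias it in either direction

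*Combined protocol and SAP*

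**What the plan says.** Section 2.0 (B1, Study Overview) states: "Cannabis use will not be targeted with treatment". The counselling text in Section 9.0 covers the co-user who nevertheless wants to reduce or stop: "standard information and resources will be provided, but this will be kept minimal to avoid researcher-imposed impact on cannabis use". It then continues: "Participants will be encouraged to pursue desired cessation, but will be reminded that the current study is focused on tobacco cessation".

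The Table 2 schedule in Section 9.0 has a row for "Cannabis Quit Interest". Its footnote says the item is "administered at screening as part of a cannabis history questionnaire, and then administered alone at subsequent visits", so a baseline value exists for co-users.

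Section 10.0, under power, describes the Aim 2 outcome: "Cannabis use during the final 4 weeks of study treatment as compared to baseline use will be assessed among co-users". Under Primary Study Aims, the Aim 2 mixed models have "nicotine dependence group as the primary model predictor". Continuous FTND (linear and quadratic) and a weekly trajectory analysis by dependence group follow. No covariate is listed. The group-based trajectory models under Secondary Data Analysis use baseline covariates to determine membership but do not say which. Motivation to quit is named only for the Aim 1 propensity score, without saying which substance is meant.

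**The concern.** Section 4.0 does not exclude co-users who intend to cut down on cannabis, and the trial gives them some support if they say so. A fall in cannabis use that a participant had already planned enters the Aim 2 outcome alongside changes that accompany the tobacco quit attempt. Every co-user receives the same tobacco treatment, so no concurrent group shows what cannabis use would have done without it.

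Aim 2 rests on a contrast between medium/high and low nicotine dependence, and those groups are not randomised. If interest in quitting cannabis differs between them, part of the contrast reflects that difference. If it does not differ, variation in quit interest still adds noise that a baseline covariate could remove. Either way, the measure that would help is collected and the Aim 2 models do not name it.

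**Working it through.** **Inputs from the documents (Section 10.0, power):** 139 co-users, 25% attrition, 104 completers, about 40% with medium/high dependence, 5% type 1 error, 80% power, Cohen's d of about 0.6. Sidedness is not stated; two-sided is assumed.

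**The plan's own figure.** 139 × 0.75 = 104.25, and 40% of 104 is about 42, leaving 62. With the normal approximation, detectable d = (1.960 + 0.842) × √(1/42 + 1/62) = 0.56; the t-based value is 0.57. This reproduces the plan's rounded 0.6. At d = 0.6 the t-based power is 84.5%. Section 5.0 gives 137 co-users instead of 139; 137 × 0.75 = 102.75 completers leaves detectable d at 0.57, so that discrepancy does not matter here.

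**Illustration A: linear confounding.** Let r be the within-group correlation between screening quit interest and fall in cannabis use, and δ the group difference in quit interest in SD units. Both are assumed. Unadjusted d = 0.6 ± r × δ. With δ = 0.3:

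| r | More interest in medium/high group | More interest in low group |
|---|---|---|
| 0.3 | 0.6 − 0.09 = 0.51, power 71.5% | 0.6 + 0.09 = 0.69, power 93% |
| 0.5 | 0.6 − 0.15 = 0.45, power 61% | 0.6 + 0.15 = 0.75, power 96% |

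The right-hand column is not a gain: the contrast is overstated.

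**Effect of adjustment.** With δ = 0, the effective d = 0.6 / √(1 − r²). For r = 0.3 this is 0.629 (power 88%); for r = 0.5 it is 0.693 (power 93%). With δ = 0.3, the imbalance itself takes up about 2% of the group information, and adjusted power is 87% to 92%.

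**Illustration B: a share q quits outright.** Assume non-quitters change by +0.6 SD (medium/high) or 0 (low), and quitters in either group change by −1.0 SD. Group means are 0.6(1 − q) − q and −q. Group variances are 1 + q(1 − q)(1.6)² and 1 + q(1 − q)(1.0)². Using 41.6 and 62.4 completers and a normal approximation:

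| q, medium/high | q, low | d | Power |
|---|---|---|---|
| 0 | 0 | 0.60 | 85% |
| 5% | 5% | 0.55 | 78% |
| 10% | 10% | 0.50 | 70% |
| 20% | 10% | 0.34 | 39% |
| 10% | 30% | 0.67 | 92% |

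Equal quitting dilutes the contrast. Unequal quitting can push it either way.

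**The case against.** The strongest reply is that Aim 2, as written, is to assess changes in cannabis use during tobacco treatment. Section 1.0 treats concurrent reduction and abstinence as things to be observed, and B1 plans separate profiles for compensation, reduction and stability. A self-chosen reduction is therefore a legitimate Aim 2 change. This stands: a reader might infer that counting such reductions is an error, but the documents do not support that. The gap is in precision and in confounding of the group contrast.

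Support for quitting cannabis is deliberately minimal, and the preliminary survey found that "while interest in quitting cannabis was low (2.4 ± 2.3 ; 10-point scale"). This also stands and limits the likely size. Under assumed distribution shapes, that mean and SD put about 10% to 18% of co-users at 5 or above, or 14 to 25 of 139. Interest is not quitting, however. If all of them cut use by 1 to 1.5 SD (assumed), a rise of 0.10 × 1.0 / 0.90 = 0.11 to 0.18 × 1.5 / 0.82 = 0.33 SD in the others would average to zero. If only a quarter to a half did so, the figure is about 0.03 to 0.15 SD.

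A reader might go further and infer that self-chosen quitting masks compensation. It lowers the mean change, but the powered contrast can move either way, and the documents do not fix the sign.

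Finally, the plan lists no covariates at all, so quit interest is not ruled out, and silence about recording resource requests does not show that they go unrecorded. That is fair: the supportable statement is that the score is not pre-specified.

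**Conclusion.** The point holds as a pre-specification gap in a secondary aim. A relevant baseline measure is collected, the Aim 2 groups are not randomised, and the Aim 2 and trajectory models do not name the measure. The plan's power figure is sound on its own assumptions.

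The consequence cannot be sized from the documents. The correlation of 0.3 to 0.5, the 0.3 SD imbalance, the share of quitters and the depth of their reduction are all assumptions. Under them, the unadjusted d of 0.6 ranges from 0.45 to 0.75 in Illustration A. With no imbalance there is no bias, and the benefit of adjustment is precision only: power of 84% becomes 88% to 93%.

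Adjustment has limits. It would not make Aim 2 a causal analysis of tobacco treatment, since there is no untreated comparison. Nor does it always recover d = 0.6. In Illustration B with 10% quitting in both groups, even an additive term for actual quitting leaves a mean difference of 0.9 × 0.6 = 0.54, because the dependence effect is absent among quitters.

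**What to change.** In Section 10.0, pre-specify the screening cannabis quit interest score as a covariate in the Aim 2 final-4-week and weekly models, and name it among the baseline predictors of trajectory-group membership. Use the screening value only: later scores may themselves be affected by treatment and should not be ordinary adjustment covariates. Where the weekly model tests slopes, a quit interest by visit term is needed for the adjustment to reach that contrast.

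If requests for cannabis-quit resources during treatment are analysed, report them descriptively. Excluding those participants would condition on a post-baseline event that the tobacco quit attempt may cause, and would selectively remove reducers. Such an analysis should not decide whether a reduction profile is accepted, because that would tilt Aim 2 towards finding compensation.

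The cost is a short SAP change and one degree of freedom per model for the main effect (one more for a linear visit interaction). It needs no new assessment, visit or participant, and no change to the counselling text. The change should be made before Aim 2 data are examined, so that the covariate is not chosen after the fact.
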